5.5.2.1 CDR

Clinical Dementia Rating Sum of Boxes (CDR-SOB) is a global scale covering both functional and cognitive domains.

The CDR-GS characterizes a participant's level of impairment according to the following categories: 0 (normal), 0.5 (very mild dementia), 1 (mild dementia), 2 (moderate dementia), and 3 (severe dementia). The Sum of Boxes score is a detailed quantitative

general index that provides more information than the CDR-GS in patients with mild dementia (Berg 1988; Morris et al. 2001; O'Bryant et al. 2010) and is scored from 0 to 18 with higher scores indicating greater impairment. The CDR characterizes six domains: memory, orientation, judgment and problem solving, community affairs, home and hobbies, and personal care. The necessary information to make each rating is obtained through a semi-structured interview with the participant and a reliable informant or collateral source (e.g., a study partner [non-professional caregiver]).

5.5.2.2 MMSE

The MMSE is a set of standardized questions used to evaluate possible cognitive impairment and help stage the severity level of this impairment (Folstein et al. 1975). The questions target six areas: orientation, registration, attention, short-term recall, language, and constructional praxis/visuospatial abilities. The MMSE is a participant-based assessment.

5.5.2.3 ADAS-Cog11 and ADAS-Cog13

The ADAS-Cog is the most frequently used scale to assess cognition in clinical trials for mild to moderate AD dementia (Rozzini et al. 2007; Connor and Sabbagh 2008; Ihl et al. 2012). More specifically, the ADAS-Cog is a patient-based assessment that measures learning and memory, language production, language comprehension, constructional praxis, ideational praxis, and orientation. The modified version will be used; it has 13 items and includes the addition of delayed word recall and a number of cancellation subtests, as well as use of only one trial for word recognition (Mohs et al. 1997). Equivalent alternate forms of the word recall, word recognition, and number cancellation subtests will be used in successive test administrations.

The ADAS-Cog 11 and 13 will be used in this study. Individual item scores are based on errors and generally range from 1 to 5, although some items have smaller or larger score ranges. The ADAS-Cog 13 total score ranges from 0-85, with higher scores reflecting greater impairment. It takes approximately 45 min to administer the ADAS-Cog 13.

5.5.2.4 Verbal Fluency Task

The category verbal fluency (e.g., animals) is a participant-based assessment that measures speed and flexibility of verbal thought. Verbal fluency tests are sensitive tools for detecting dementia (Pasquier et al. 1995; Lezak et al. 2004) and for monitoring decline over time (Clark et al. 2009).

5.5.2.5 Coding

The Coding, also called Digit Symbol Substitution Test (or DSST), is a subtest from the Wechsler Adult Intelligence Scale-Fourth Edition (WAIS-IV; Wechsler 2008). The Coding is a participant-based assessment that measures speed of processing and associative memory. The test is known to be sensitive to disease progression (Lezak et al. 2004). The 120-second version of the test will be used in this study.

5.5.2.6 ADCS-ADL

The ADCS-ADL ([Galasko et al. 1997](#)) is the scale most widely used to assess functional outcome in participants with AD ([Vellas et al. 2008](#)). The ADCS-ADL is a 23-item informant-based questionnaire that covers both basic activities of daily living (ADL) (e.g., eating and toileting) and more complex ADL or instrumental ADL (e.g., using the telephone, managing finances, preparing a meal). It has a 4-week recall period. Total scores range from 0-78, with higher scores indicating better functioning.

5.5.3 Home Administration Questionnaire (Patient)

As described in Section [5.4](#), the home administration questionnaire contains 2 items to be completed by participants. Participants will complete satisfaction and convenience items on a 4-point verbal Likert scale and respondents will be asked to consider their most recent at home administration in answering these questions. Responses to this questionnaire may be captured electronically and transferred to the database directly from the core laboratory.

5.5.4 Biomarker Analyses

5.5.4.1 Volumetric MRI Analyses

Analysis of volumetric MRI will be based on the MRI-mITT analysis set.

Volumetric MRI, for each brain region, will be summarized visit using descriptive statistics for the absolute volume at baseline and percent change from baseline at post-baseline visits. These summaries will be provided for both the MRI-mITT and the MRI-longitudinal analysis sets.

A MMRM analysis will be used to estimate the mean percent change from baseline to Week 104 (as well Week 48) in volumetric MRI for each brain region. The model will include the percent change from baseline in volumetric MRI as the dependent variable, while adjusting for visit (as categorical), baseline age, gender (as categorical), APOE ε4 status (as categorical; carrier vs. non-carrier) and disease stage (as categorical). Visit will be treated as the repeated variable within a participant. An unstructured variance-covariance matrix will be applied to model the within-participant errors; in the case of non-convergence, compound symmetry will be used, together with a robust estimator of standard error (“sandwich” estimator).

There will be no data imputation for missing data. However, the MMRM provides unbiased estimates and valid inference in the presence of missing data, under the MAR (missing at random) assumption.

The following brain regions will be considered:

- Whole brain volume
- Regional brain volumes
- Ventricular volume

Other exploratory analyses based on other brain regions may be reported separately.

In addition, exploratory biomarker analysis will be performed to assess change from baseline to Week 104 in functional brain connectivity, fiber tract integrity, and cerebral blood perfusion.

5.5.4.2 Plasma Biomarker Analyses

Exploratory fluid plasma biomarkers will be assessed at each visit for tau and amyloid pathology as well as neurodegeneration, including, but not limited to, the following:

- p-tau
- A β 1-42
- Neurofilament light chain (NFL)
- Glial fibrillary acidic protein (GFAP)

The plasma concentration of these biomarkers will be assessed. Analysis of plasma biomarkers will be based on the ITT analysis set. Biomarker data will be summarized for each assessment visit using descriptive statistics of absolute values as well as change from baseline values.

An MMRM analysis will be used to estimate the mean change from baseline to Week 104 (but also to Week 24, 36, 52, and 76) for each plasma biomarker. The model will include the change from baseline in the plasma biomarker as the dependent variable, while adjusting for visit (as categorical), APOE ϵ 4 status (as categorical; carrier vs non-carrier), baseline biomarker and baseline biomarker-by-visit. Visit will be treated as the repeated variable within a participant. An unstructured variance-covariance matrix will be applied to model the within-participant errors; in case of non-convergence, compound symmetry will be used, together with a robust estimator of standard error ("sandwich" estimator). The MMRM model will be based on log-transformed biomarker data.

There will be no data imputation for missing data. However, the MMRM provides unbiased estimates and valid inference in the presence of missing data, under the MAR (missing at random) assumption.

Other exploratory plasma biomarkers may be reported separately.

5.6 SAFETY ANALYSES

Descriptive statistics will be used to analyze all safety data collected in SE analysis set, unless otherwise specified. Safety data collected during the safety follow-up will also be included but may be summarized in separate tables. Safety analyses will be assessed through summaries of exposure to study treatment, adverse events, changes in laboratory test results, MRI findings, changes in vital signs and ECGs, changes in C-SSRS scores and immunogenicity.

5.6.1 Extent of Exposure

Exposure to study drug information will be descriptively summarized overall and by dose level as follows:

- Treatment duration (in weeks)
- Total cumulative study drug dose (mg)
- Total number of study drug administrations
- Medication errors

5.6.2 Adverse Events

All verbatim Adverse Events (AE) terms will be coded using the Medical Dictionary for Regulatory Activities (MedDRA) version that is current at the time of the analysis (Version 24.1 or higher), and AE intensity will be graded according to the scale defined in Table 2 in Section 5.3.3 of the study protocol (mild/moderate/severe). The frequency of each AE preferred term will be defined as the number of participants experiencing at least one occurrence of the event. Each table will present the overall number and percentage of participants experiencing at least one AE and the total number of AEs reported. Percentages will be based on the number of participants in the SE analysis set. In summary tables, AEs will be sorted by body system (also referred to as System Organ Class, in decreasing order of overall incidence), then by preferred term (in decreasing order of overall incidence). The summary tables will be restricted to treatment-emergent AEs, i.e., AEs that occur on or after the day of first study drug, and to those AEs with onset no later than 17 weeks after last dose of study drug.

Non-treatment-emergent AEs (with onset before the first dose) will be listed, and AEs occurring more than 17 weeks after the last dose will be summarized.

The following safety information will be summarized for treatment-emergent AEs:

- AEs, AEs by greatest intensity, AEs related to study drug, AEs related to radioligand
- SAEs, SAEs by greatest intensity, SAEs related to study drug
- AEs leading to discontinuation of study drug
- AEs leading to dose modification (dose interruption, dose reduction, or delayed up-titration). Delayed up-titration at any given visit is defined as the simultaneous occurrence of the following two tickboxes in the eCRF Adverse Events form:
 - Action taken with Gantenerumab due to AE/SAE: Dose Not Changed
 - Was dose regimen modified from protocol schedule? Yes
- AEs resulting in death
- Injection site reaction (ISR) signs and symptoms
- Systemic injection reactions (AEs with eCRF tickbox “systemic injection reaction” selected)
- Hypersensitivity AEs
- AEs associated with medication errors, AEs of medication errors

The impact of the COVID-19 pandemic on the safety data will be assessed by reviewing the following:

- Confirmed or suspected COVID-19 AEs
- AEs associated with COVID-19
- Potential long COVID-19 symptoms

The following data handling rules will be applied for all AE summary tables:

- Events that are missing both at onset and at end dates will be considered to have started after the first dose of study drug and the duration will be set to missing.
- If the onset date is missing, and the end date is on or after the first dosing date or unresolved or missing, then the event will be considered to have started after the first dose of study drug.

The following data handling rules will also be applied for specific tables:

- An AE will be included in the summary table of AEs leading to study drug discontinuation if the “action taken with Gantenerumab due to SAE/AE” drop-down menu on the AE eCRF is checked “drug withdrawn”.
- In the summary table of AEs by intensity, if a participant has more than one occurrence of an event, the event with the most severe intensity will be counted. If the intensity of an AE is missing, then the AE will be included only in the total number of events column, and not in the count of participants with the event by intensity.
- In summary tables of AEs related to study drug, if a participant has more than one occurrence of an event, the related event will be counted if applicable. If the relationship of an AE is missing, then the AE will not be included.

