5.3.4 Assessment of Causality of Adverse Events

Investigators should use their knowledge of the participant, the circumstances surrounding the event, and an evaluation of any potential alternative causes to determine whether an adverse event is considered to be related to the study drug, indicating "yes" or "no" accordingly. The following guidance should be taken into consideration:

- Temporal relationship of event onset to the initiation of study drug
- Course of the event, with special consideration of the effects of dose reduction, discontinuation of study drug, or reintroduction of study drug (as applicable)
- Known association of the event with the study drug or with similar treatments
- Known association of the event with the disease under study
- Presence of risk factors in the participant or use of concomitant medications known to increase the occurrence of the event
- Presence of non-treatment-related factors that are known to be associated with the occurrence of the event

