3. SAMPLE SIZE DETERMINATION

Determination of sample size is relative to the sample of participants assessed by amyloid PET imaging using florbetaben. The sample size for this study is determined as the number of participants needed for the estimated change from baseline to Week 104 in amyloid PET load to fall into a 10 CL confidence interval (CI) around its true value. With a standard deviation of 25.67 CL (see below), 150 participants are required to fulfill this criterion. However, due to a lower than expected screen failure rate at the end of the enrollment period, a total of 192 participants have been enrolled.

The standard deviation of amyloid reduction was estimated using amyloid PET data from the ongoing Studies WN25203 (hereafter referred to as “SCarlet RoAD”) and WN28745 (hereafter referred to as “Marguerite RoAD”) open label extension (OLE) periods (based on a cutoff date of 14 October 2019), yielding a value of 25.67 CL.

Uncertainties of the parameters affecting the estimation (e.g., drop-out rate, study drug discontinuation rate, and standard deviation) were assumed to be equivalent to a decrease in sample size of up to around 35% and were corrected for accordingly. This drop-out rate is calculated based on Marguerite RoAD OLE at Week 104 that was ongoing at the time the study protocol was written. A sample size increase may be considered if factors external to the study would warrant a change to the sample size assumption.

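### AEs with a missing relationship are left out of the drug-related tables while the participant stays in the denominator, so the rule can lower the related-AE incidence but never raise it

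*SAP*

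**What the plan says.** SAP Section 5.6.2 sets rules for incomplete AE records. For the tables of AEs related to study drug it states: "If the relationship of an AE is missing, then the AE will not be included". The denominator is fixed in the same section: "Percentages will be based on the number of participants in the SE analysis set". The planned summaries include AEs related to study drug and also "SAEs, SAEs by greatest intensity, SAEs related to study drug", but the missing-relationship sentence names only AEs, so its reach to the related-SAE table is left to the reader.

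The neighbouring rules are these:
- Both dates missing: "Events that are missing both at onset and at end dates will be considered to have started after the first dose of study drug".
- Onset missing, with the end date on or after first dosing, missing, or the event unresolved: "then the event will be considered to have started after the first dose of study drug".
- Intensity missing: "If the intensity of an AE is missing, then the AE will be included only in the total number of events column".

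Protocol Section 5.3 asks the investigator to assess causality for each recorded AE, and Protocol Section 5.3.4 makes the answer a plain yes or no, with no unknown category. SAP Section 5.8.1 applies Section 5.6.2 to the interim report as well as the primary one.

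**The concern.** Because causality has only two answers and the denominator does not change, leaving an event out of the related table has the same numerical effect as recording it as not related. The omission also leaves no trace: no row, footnote or count tells a reader of the related-AE table whether none or several events were left out.

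The study has a single arm, so the drug-related tables are read as absolute rates and no control arm shares the error. What is at stake is whether a reader of the interim or primary report can take the related-AE figures at face value.

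**Working it through.** The plan states no figure that depends on this rule, so there is nothing to reproduce. The check is about direction first and size second.

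**Inputs**
- Enrolled: "a total of 192 participants have been enrolled" (SAP Section 3). The safety-evaluable set is those enrolled who received at least one dose (SAP Section 4), so n is at most 192. Its exact size is not given.
- Causality: yes or no for each AE (Protocol Sections 5.3 and 5.3.4).
- Number of AEs with missing causality: not in the documents. An assumed range is used below.

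**Direction.** Let R be the participants with at least one AE marked related. Let k be the participants with no AE marked related but at least one whose relationship is missing. Let t be those among the k whose event the investigator would have marked related, so 0 ≤ t ≤ k.

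- SAP rule reports R/n.
- Complete data would give (R + t)/n.
- Counting missing as related reports (R + k)/n.

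Hence R/n ≤ (R + t)/n ≤ (R + k)/n. The SAP rule errs by −t/n, which is never positive. The alternative errs by (k − t)/n, which is never negative.

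**Size.** With n = 192, one participant is 1/192 = 0.52 percentage points. If fewer than 192 were dosed, each is worth slightly more. For assumed values of k, the gap between the two rules is 100 × k/192:

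| k (assumed) | Gap, percentage points |
|---|---|
| 0 | 0 |
| 1 | 0.52 |
| 2 | 1.04 |
| 5 | 2.60 |
| 10 | 5.21 |

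These are upper limits on the understatement; it reaches them only if t = k.

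**Why k is smaller than the number of participants with a missing answer.** A participant with any other related AE is already in R. Protocol Section 5.3.5.2 defines injection reactions as events judged related to the injection, and Protocol Section 5.1.1.2 reports injection-site reactions in 36.4% and 40.0% of participants in the two earlier open-label extensions. Suppose, as an illustration, that those rates carry over and are independent of missing causality. Then 5 participants with a missing answer leave 5 × (1 − 0.364) = 3.18 or 5 × (1 − 0.400) = 3.00 outside R, that is 1.66 or 1.56 points instead of 2.60.

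**Other cells.** In a preferred-term row, the participant is lost unless another occurrence of that same event is marked related, so the row can be affected when the overall incidence is not. In the total number of related events, every omitted AE lowers the count by one.

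**The case against.** The strongest reply is that the case should hardly arise. Causality is required for every AE, Protocol Section 7.1 has the sponsor query discrepant data, and serious events are reported within 24 hours and evaluated by the sponsor, with causality feeding the reporting decision (Protocol Sections 5.4.2 and 5.7). Nothing disappears from the report either: the event stays in the all-AE tables and, where it applies, in the SAE, discontinuation, dose-modification and death tables. ARIA, an identified risk, is analysed mainly from MRI findings rather than from investigator causality (SAP Section 5.6.3). SAP Section 2 tests no hypothesis. Finally, counting every missing answer as related exchanges a possible downward error for a possible upward one.

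All of this stands, and it sets the size of the point. It does not defend the rule itself. If no answers are missing, the changed sentence has no effect; if some are, the present sentence errs in one direction and does not show it. The upward error of the alternative is visible once the number of such events is footnoted.

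A reader might also infer that the SAP contradicts itself, since missing dates are resolved towards inclusion and missing causality towards exclusion. The documents do not support that. The date rules decide whether an event is treatment-emergent and so enters the summary tables at all. Intensity and causality are attributes of events already counted, and the missing-intensity rule does not assign the worst case either: the event is left out of the participant count by intensity. The real difference is narrower. The intensity rule keeps the event visible in a total column, and the relationship rule does not.

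**Conclusion.** The point holds as a minor one. The rule in SAP Section 5.6.2 treats a missing relationship as not related, and its effect on the drug-related incidence is zero or downward. The size is 0.52 percentage points for each participant with no other related AE, taking n = 192. The number of such participants is unknown, probably small and possibly zero, so every multiple of 0.52 shown above rests on an assumption. The effect is confined to the drug-related tables.

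A reader might infer that the interim report is especially exposed because it uses a data cut. The documents do not show this. SAP Section 5.8.1 sets the cut-off at 30 June 2022, ahead of the pivotal studies' expected last visit on 23 September 2022, expressly to leave time for cleaning. Nothing in either document indicates that causality would be incomplete at that date.

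**What to change.** In SAP Section 5.6.2, replace the missing-relationship sentence with one to this effect: *An AE whose relationship to study drug is missing is counted as related to study drug.* State that the same rule governs the table of SAEs related to study drug. Footnote each affected table with the number of AEs counted as related for this reason. It would also help to say whether the rule covers the AEs related to radioligand, which the section lists but the sentence does not mention.

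The cost is one sentence and a footnote. The related-AE count may be slightly higher and could include some events that were not related; the footnote lets a reader see how many and subtract them.

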5.6.3 MRI Safety Findings

ARIA-E and ARIA-H are identified risks associated with gantenerumab. According to the study protocol, not every ARIA finding qualifies as an adverse event. An ARIA finding must be reported as an adverse event if it meets any of the following criteria:

- Symptomatic ARIA-E (i.e., onset or worsening of CNS symptom(s) that is/are temporally associated with ARIA-E MRI findings), and/or
- ARIA findings that result in a change in study treatment (e.g., dose modification, treatment interruption, or treatment discontinuation), and/or
- Findings that are otherwise clinically significant in the investigator's judgment

Any accompanying symptoms should also be captured as separate adverse events.

Since not all ARIA MRI findings qualify as AE, ARIA analyses will be mainly based on ARIA MRI findings. ARIA AEs will also be reported. Based on MRI data, the incidence, severity (based on the Barkhof Grand Total Score [BGTS]), and timing of ARIA-E and the incidence and timing of ARIA-H will be summarized overall and also by APOE ε4 genotype (by number of alleles) and by dose level. The timing of ARIA-E and ARIA-H

may be summarized by descriptive statistics and Kaplan-Meier methods. Recurrence of ARIA-E will be summarized overall and also by APOE $\epsilon 4$ genotype (by number of alleles). ARIA-E associated with CNS symptoms (see Section 5.6.3.1) and with serious CNS symptoms will be summarized by APOE $\epsilon 4$ genotype. Temporal co-occurrence of ARIA-E and ARIA-H will be summarized overall and also by APOE $\epsilon 4$ genotype. Temporal co-occurrence is defined as an MRI scan showing new ARIA-H that occurs between ARIA-E onset and resolution (inclusive), irrespective of the brain region.

MRI findings other than ARIA will also be summarized.

The summaries of MRI safety findings will be produced using the SE analysis set with at least one post-baseline MRI (M-SE, see Section 4).

